## 10.5 OBLIGATIONS OF THE SPONSOR

During the course of the study, the Sponsor will report in an expedited manner:

- All SAEs that are both unexpected and at least reasonably related to the IMP (Suspected Unexpected Serious Adverse Reactions, SUSAR), to the regulatory authorities, independent ethics committees (IECs)/institutional review boards (IRBs) as appropriate and to the Investigators.
- All SAEs that are expected and at least reasonably related to the IMPs to the regulatory authorities, according to local regulations.

In this study, some AEs are considered related to the underlying condition and thus will not be considered unexpected as given in the IB.

Any other AE not listed as an expected event in the Investigator's Brochure or in this protocol will be considered unexpected.

The Sponsor will report all safety observations made during the conduct of the trial in the clinical study report.

## 10.6 SAFETY INSTRUCTIONS

### 10.6.1 Local injection site reactions (non-allergic or allergic not requiring consultation)

The classification of local injection site reactions, the reporting time frame, and the corresponding complementary forms in the e-CRF to be filled are summarized in [Appendix H](#).

In case the Investigator or the patient recognizes any signs of local intolerance, the patient should be treated and followed-up as per the Investigator's medical judgment.

Specific e-CRF screens (General Allergic Reaction and/or Local Injection Site Reaction Complementary Form) are to be filled ([Appendix E](#)). The local symptoms should be reported in the "local injection site reaction" section of the complementary form. If the injection site reaction progress/expand/worsen/etc, both "local injection site reaction" and "general allergic reaction" of the complementary form should be completed.

Sometimes transient injection site reactions, irritant in nature, may occur, requiring no intervention and being of dubious significance. These reactions would not be considered to be allergic reactions.

Under certain circumstances, no AE of local injection site reactions should be reported, as this is not typically considered a clinically important finding:

The patient has erythema, redness, and/or swelling, that is <2.5 cm in diameter, AND

- The swelling does not interfere with activity, AND
- No other signs or symptoms are involved.

Note: if the patient has a reaction of swelling with a diameter <2.5 cm that interferes with activity, it should be considered as a clinically relevant finding and should be reported as an AE with a corresponding intensity of moderate or severe, in accordance with [Appendix E](#).

### **10.6.2 Allergic Adverse Events**

Specific eCRF screens are to be filled in to assess allergic reactions or allergic-like reactions that may occur during the clinical studies conducted with alirocumab.

Sometimes transient injection site reactions, irritant in nature, may occur, requiring no intervention and being of dubious significance. These reactions would not be considered to be allergic reactions.

Adverse events that may constitute an allergic reaction (eg, generalized itch, nasal itch, swelling at injection site, flushing, hives, swelling at lips, eyes, face, tongue, hands, feet, lump in throat, difficulty to swallow, hoarseness, change in pitch of voice, incapacity to speak, wheezing, chest tightness, stridor, etc) should be considered to be reported on the General Allergic Reaction and/or Local Injection Site Reaction Complementary Form.

Adverse events that are obviously not of allergic origin (eg, local injection site reactions related to mechanics of injection) should only be recorded on the Local Injection Site Reaction Complementary Form. However, injection site reactions that progress/expand/worsen/etc should be evaluated as recommended in [Section 10.6.3](#) and General Allergic Reaction Complementary form should be completed.

The IMP should be immediately interrupted (temporarily discontinued) if there is a suspicion of an allergic event related to IMP. See [Section 10.3.1](#) for further information on treatment interruption and [Section 10.3.2](#) for criteria for permanent treatment discontinuation.

### **10.6.3 Allergic adverse event with cutaneous involvement**

Adverse events with cutaneous involvement which are obviously of allergic origin or injection site reactions which progress/expand/worsen/etc. should be evaluated by a dermatologist as soon as possible, and preferably within one week of the site first becoming aware of the event.

The Investigator should evaluate the patient for possible etiologies (new medications, etc.) and extracutaneous symptoms and signs. An unscheduled Local Laboratory assessment for hematology, chemistry, liver panel should be obtained. If it is possible, the site will take pictures of the skin lesions in order to provide the patient with them for the dermatologist's visit. If the photos are obtained, then copies should be kept as source documents which may later be collected by the sponsor. The Investigator will provide a summary of the patient's case, reason for consultation, and information being requested to the consulting dermatologist.

A full consultation report should be sent by the dermatologist to the Investigator. The full report should contain, at a minimum, the following information; a detailed description of the rash (such as the morphology [lesion type], shape of individual lesions, arrangement of multiple lesions [eg, scattered, grouped, linear], distribution, color, consistency, presence of pruritus or pain, and other clinical signs) and in case a skin biopsy (including histopathology and immunofluorescence) was done (if it was deemed necessary as per the dermatologist's or Investigator's medical judgment), the results of this investigation with, if applicable, a specific diagnosis of the AE. The Investigator will fax the full report and the corrected AE form if necessary, to the Monitoring Team Representative within 24 hours.

#### **10.6.4 Acute allergic injection reactions**

Acute allergic injection reaction (which are considered under the category of general allergic reactions) is defined as any AE that occurs during or shortly after injection of the IMP (characterized by but not limited to hypotension, bronchoconstriction, urticaria, edema, angioedema, nausea, vomiting). Emergency equipment and medication for the treatment of these potential adverse effects (eg, antihistamines, bronchodilators, IV saline, corticosteroids, acetaminophen, and epinephrine) must be available for immediate use for the injections at the training, and inclusion visits.

Patients will be observed at the investigational site for at least 30 minutes following the injection that takes place at the inclusion visit. Patients should be treated symptomatically if any AEs are observed. Patients are to remain at the site until any acute injection reaction is assessed as stable, per the Investigator's discretion. General Allergic Reaction and/or Local Injection Site Reaction Complementary Form will have to be completed.

#### **10.7 ADVERSE EVENTS MONITORING**

All events will be managed and reported in compliance with all applicable regulations, and included in the final clinical study report.

## 11 STATISTICAL CONSIDERATIONS

The material of this Section is the basis for the Statistical Analysis Plan for the study. This plan may be revised during the study to accommodate clinical trial protocol amendments and to make changes to adapt to unexpected issues in study execution and data that affect planned analysis. Thus a final plan should be issued before database lock.

### 11.1 DETERMINATION OF SAMPLE SIZE

No formal sample size calculation has been done. The Safety analyses of this study will be descriptive. The table below provides the precision (95% CI) associated to a variety of AE event rates for a targeted sample size of 1300 patients:

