**Table 1 - Expected 95% CI for various event rates**

Adverse event rates	10%	20%	30%	40%	50%
95%CI	[8.4%; 11.6%]	[17.8%; 22.2%]	[27.5%; 32.5%]	[37.3%; 42.7%]	[47.3%; 52.7%]

For a rare non observed event, by using the rule of three, it can be estimated that the upper limit of the 95% confidence interval of the event rate is approximately 0.23% (1 per 433).

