##### **11.4.2.1 Analysis of adverse events**

Adverse event incidence tables will be presented by system organ class (SOC), high-level group term (HLGT), high level term (HLT) and preferred term (PT) sorted in alphabetical order, the number (n) and percentage (%) of patients experiencing an AE. Multiple occurrences of the same event in the same patient will be counted only once in the tables within a treatment phase.

The denominator for computation of percentages will be the safety population.

Adverse event incidence table will be provided for all types of TEAEs: all TEAEs, all treatment emergent AESI, all treatment emergent SAEs and all TEAEs leading to permanent treatment discontinuation.

If any clinically significant signal is detected and need further characterization or for adverse event of clinical interest, exploration of time to onset could be performed for these selected TEAEs as described below to account for the differential exposure time in all patients.

Selected TEAEs will be also analyzed using time-to-event approach (Kaplan-Meier methodology). Time from the first dose of IMP injection to the first occurrence of the event will be calculated (only the first event will be counted). Patients without any event will be censored at the end of the TEAE period. Incidence rates at different time points of exposure will be presented and Kaplan-Meier curves will be provided.

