**Table 2 - Protocol amendment statistical changes**

Amendment Number	Date Approved	Rationale	Description of statistical changes
Clinical Trial Amendment no. 5 (ie, the first global protocol amendment)	01Mar2016	
Reassessment of the number of patients planned to be enrolled from 1100 initially planned to 1300
 
Streamlining of the requirements for the end of study
 
Standardization across the protocols for observational studies
 
Clarification regarding the LDL-C assessment given that efficacy is a secondary endpoint and that no central lab is utilized in this study
 
Although there is no formal interim analysis, some statistical analyses might be performed before the end of the study in order to support a dossier of reimbursement if required by health authorities in some countries
	
Modifications of the table of expected 95% CI for various adverse events rates
 
Only one final on-site visit called “EOT/EOS Visit” is required
 
Modification of the list of the AE of special interest
 
The Friedewald formula to assess LDL-C will be used even in case TG is elevated (>400 mg/dL)
 
Some statistical analyses might be performed before the end of the study

In addition to the medical history of specific interest to be described such as quoted in the protocol (CHD, CHD risk equivalents...), the multiple manifestations of CV disease (see [Section 2.1.1](#)) was added due to the very high risk of CV event profile of patients enrolled in this study.

Some secondary efficacy analyses were added compared to the original version of the protocol, mainly regarding the occurrence of very low LDL-C level and the associated changes in treatment (see [Section 2.4.4.4](#)) in order to better characterize these cases.

Additional descriptive analyses were added to document the adherence to statins according to alirocumab dose and the achieved LDL-C.

Two subgroups that are of particular clinical interest due to the very high risk of CV event profile of these patients were added, namely primary CVD prevention and the subgroup of patients with multiple manifestations of CV diseases.

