### ***Analysis of all treatment-emergent adverse events***

The following TEAEs summaries will be generated for the safety population.

- Overview of TEAEs, summarizing number (%) of patients with any
  - Treatment-emergent adverse event,
  - Serious TEAE,
  - Treatment-emergent adverse event leading to death,
  - Treatment-emergent adverse event leading to permanent treatment discontinuation.
- All TEAEs by primary SOC, HLT, HLT, and PT.
- All TEAEs by primary SOC, HLT, HLT, and PT, showing number (%) of patients with at least 1 TEAE sorted by the SOC internationally agreed order. The other levels (HLT, HLT, PT) will be presented in alphabetical order.
- All TEAEs by primary SOC and PT, showing the number (%) of patients with at least 1 TEAE by primary SOC and PT, sorted by the internationally agreed SOC order and by decreasing incidence of PTs within each SOC. This sorting order will be applied to all other tables, unless otherwise specified.
- All TEAEs by PT, showing the number (%) of patients with at least 1 TEAE, sorted by decreasing incidence of PTs.
- All TEAEs regardless of relationship (in one column of the table) and related to alirocumab according to investigator's opinion (in a second column) by primary SOC, HLT, HLT and PT, showing the number (%) of patients with at least 1 TEAE, sorted by the internationally agreed SOC order. The other levels (HLT, HLT, PT) will be presented in alphabetical order.
- All TEAEs by maximal severity, presented by primary SOC and PT, showing the number (%) of patients with at least 1 TEAE by severity (ie, mild, moderate, or severe), sorted by the sorting order defined above.
- The event rate per patient-year (the number of patients with an event in question divided by total patient-years) will be provided for all TEAEs by SOC and PT. For a patient with event, patient year is censored at time of first event; for patient without event, it corresponds to length of TEAE period.
- Kaplan-Meier curves will be provided, when appropriate, for time from first dose of alirocumab to the first occurrence of selected TEAEs as well as incidence rates at 24 weeks of exposure. Patients without any event will be censored at the end of the TEAE period. Selected TEAEs will be all AESIs (as defined in [Section 2.1.4.1](#)).

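### AE-rate precision is the only quantitative support given for N = 1300, yet the planned primary safety analysis names no confidence interval; the 0.23% zero-event limit should be labelled one-sided

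*Protocol*

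**What the plan says.** **Basis for N.** Protocol 11.1 states: "No formal sample size calculation has been done. The Safety analyses of this study will be descriptive". It goes on: "The table below provides the precision (95% CI) associated to a variety of AE event rates for a targeted sample size of 1300 patients". It then gives the two-sided intervals of Table 1 for AE rates of 10% to 50%, and a rule-of-three upper limit for an event that is never observed, "approximately 0.23% (1 per 433" patients). SAP 1.3 repeats the table and writes the limit as 3 divided by the expected number of patients. SAP Table 2 gives the background to the figure of 1300: "Reassessment of the number of patients planned to be enrolled from 1100 initially planned to 1300"; the accompanying statistical change was to update the CI table.

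**Primary analysis.** Protocol 9.1 limits the primary endpoints to safety. Protocol 11.4.2.1 presents AEs as "the number (n) and percentage (%) of patients experiencing an AE", with Kaplan-Meier analysis for selected TEAEs. SAP 2.4.5.1 begins with "Overview of TEAEs, summarizing number (%) of patients with any" TEAE, serious TEAE, TEAE leading to death or TEAE leading to permanent discontinuation. It adds event rates per patient-year, Kaplan-Meier curves with 24-week incidence for the AESIs, and injection site reactions per injection. No confidence interval is named for any of these.

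**Secondary analysis.** Protocol 11.4.3 and SAP 2.4.4.2 give 95% CIs for the LDL-C target proportions. SAP 2.4.4.2 and 2.4.4.4 also give them for titration patterns, treatment changes after very low LDL-C, alirocumab discontinuation and statin changes.

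**The concern.** The one design property the documents put a number on is how precisely an AE rate will be known at 1300 patients. The analysis plan never schedules that precision for reporting. Calling the study descriptive does not explain the gap, because SAP 2.4 applies the same description to every analysis and the secondary proportions still get intervals.

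At stake is the reading of uncommon events. Table 1 starts at 10%, but Protocol section 4 reports, for the alirocumab arm of the largest prior study it summarises, TEAEs leading to death in 0.5% and to discontinuation in 6.2%. Both are below the range of the table. For an AESI with no events, the upper limit is the only informative number, and the plan does not produce it.

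A second, smaller matter is that Table 1 and the zero-event limit are both called 95% confidence intervals but rest on different tail areas, and the text does not say so.

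**Working it through.** **Inputs.** n = 1300, AE rates of 10% to 50%, and the stated zero-event limit of 0.23% (Protocol 11.1, SAP 1.3).

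**Step 1: reproduce Table 1.** Two-sided normal-approximation interval, p ± 1.96 × sqrt(p(1 − p)/1300).

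| p | Half-width | Computed | Stated |
|---|---|---|---|
| 10% | 1.63 | 8.37 to 11.63 | 8.4 to 11.6 |
| 20% | 2.17 | 17.83 to 22.17 | 17.8 to 22.2 |
| 30% | 2.49 | 27.51 to 32.49 | 27.5 to 32.5 |
| 40% | 2.66 | 37.34 to 42.66 | 37.3 to 42.7 |
| 50% | 2.72 | 47.28 to 52.72 | 47.3 to 52.7 |

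All five match. The table puts 2.5% in each tail. An exact (Clopper-Pearson) interval at 10% would be 8.42 to 11.76, so the table is not exact.

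**Step 2: set the planned outputs side by side.**

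| Output | Section | 95% CI named? |
|---|---|---|
| AE incidence, TEAE overview | Protocol 11.4.2.1, SAP 2.4.5.1 | No |
| TEAE and serious TEAE rates per patient-year | SAP 2.4.5.1 | No |
| 24-week Kaplan-Meier incidence, AESIs | SAP 2.4.5.1 | No |
| AESI tables | SAP 2.4.5.1 | No |
| LDL-C target proportions | Protocol 11.4.3, SAP 2.4.4.2 | Yes |
| Titration proportions | SAP 2.4.4.2 | Yes |
| Changes after very low LDL-C, alirocumab discontinuation, statin changes | SAP 2.4.4.4 | Yes |

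The nearest thing to a safety interval is alirocumab discontinuation by reason, which SAP 2.4.4.4 places under additional efficacy analyses.

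**Step 3: size for a rare event.** As an illustration, take the 0.5% seen for TEAEs leading to death in the prior study: 0.005 × 1300 = 6.5, so say 7 events. Then 7/1300 = 0.54%, with a two-sided exact 95% CI of 0.22% to 1.11%. The upper limit is about five times the lower one, and the count and percentage alone do not show this.

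**Step 4: the zero-event limit.**
- Rule of three: 3/1300 = 0.2308%, or 1 per 433. This reproduces the stated figure.
- Exact one-sided 95% limit: 1 − 0.05^(1/1300) = 0.2302%, or 1 per 434. The rule of three approximates this limit, with the full 5% in the upper tail.
- Exact two-sided 95% limit: 1 − 0.025^(1/1300) = 0.2834%, or 1 per 353.
- Ratio of the exact limits: 0.2834/0.2302 = 1.23. The difference is 0.05 percentage points.
- Patients needed, with no events, for a two-sided limit equal to 3/1300: ln(0.025)/ln(1 − 3/1300) = about 1597.

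**The case against.** The strongest reply is that the study has one arm, no hypothesis test and a declared descriptive safety analysis, and that part of its primary objective is simply access to the drug. With n and N printed, any reader can compute a binomial interval. That stands for simple proportions, and it makes the gap one of reporting rather than lost information. It does not carry over to a Kaplan-Meier incidence, whose interval cannot be recovered from the point estimate alone. Nor does it cover a patient-year rate with zero events, where the person-time cannot be worked back from the rate.

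A second reply is that treatment lasts from 12 weeks to 30 months (Protocol 6.2.1), so a binomial interval on a crude proportion ignores unequal exposure. This also stands. It is a reason to put intervals on the exposure-adjusted outputs as well, not to omit them.

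A third is that 0.23% is exactly what the named rule gives, is stated as approximate, and follows a common convention, since with no events the lower limit is fixed at 0. This stands in full: the basis is unlabelled, and the figure is not an arithmetic error.

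Finally, the SAP names Clopper-Pearson only for certain proportions in its efficacy sections, and only when numbers are deemed insufficient. So the SAP does not contradict a method of its own here; using it for AEs is a proposal.

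**Conclusion.** The plan has a real but modest gap. The precision offered in support of 1300 patients is not scheduled for reporting in the primary analysis, while secondary proportions get intervals with no reason given for the difference. It matters most for events under about 1% and for AESIs with none. The zero-event label is a minor companion: 0.23% against 0.28%, with no decision rule attached.

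Three stronger readings are tempting and not supported:
- *The trial was sized on CI width and fails its own sizing.* Both documents disclaim a formal calculation, no target width is stated, and the amendment table shows the CI table being updated to fit a reassessed enrolment figure.
- *The AE analysis is counts and percentages only.* Patient-year rates, Kaplan-Meier incidences and events per injection are planned; what they lack is an interval.
- *The documents claim to exclude event rates above 0.23%.* They say only that the limit can be estimated at about that value.

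The figures assume a safety population of 1300; the actual denominator will change them slightly. The 7-event case is illustrative, not a forecast.

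**What to change.** In SAP 2.4.5.1:
1. Add two-sided exact (Clopper-Pearson) 95% CIs to the four TEAE overview proportions: any, serious, leading to death, leading to permanent discontinuation.
2. Add the same interval to each AESI, including those with zero events.
3. Give 95% CIs, with the method named, for the patient-year rates and 24-week Kaplan-Meier incidences already planned.

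In Protocol 11.1 (and its synopsis) and SAP 1.3, either label 0.23% (1 per 433) as a one-sided 95% limit, or give the two-sided exact limit of 0.28% (1 per 353) to match Table 1.

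The cost is one column in existing tables and, if the second wording is chosen, a slightly less favourable figure. No new data are needed. Protocol section 11 allows the analysis plan to be revised and calls for a final plan before database lock.

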**Table 1 - Expected 95% CI for various event rates**

Adverse event rates	10%	20%	30%	40%	50%
95%CI	[8.4%; 11.6%]	[17.8%; 22.2%]	[27.5%; 32.5%]	[37.3%; 42.7%]	[47.3%; 52.7%]

For a rare non observed event, by using the rule of three, it can be estimated that the upper limit of the 95% confidence interval of the event rate is approximately 0.23% (1 per 433).

### 11.2 DISPOSITION OF PATIENTS

Screened patients are defined as any patient who met the inclusion criteria and signed the informed consent.

Enrolled patients consist of all screened patients, with a treatment kit number allocated and recorded in the IVRS/IWRS database, regardless of whether treatment kit was used or not.

Reasons for treatment discontinuation as well as reasons for withdrawal from the study will be summarized.

## 11.3 ANALYSIS POPULATIONS

### 11.3.1 Efficacy population

#### 11.3.1.1 *Modified intent-to-treat population*

Modified intent-to-treat population (mITT): all enrolled patients who took at least one dose or part of a dose of alirocumab and had an evaluable efficacy endpoint during the efficacy treatment period. The main efficacy endpoint will be evaluable provided that the two following conditions are met:

- Availability of a baseline calculated LDL-C value (last value available prior to the first injection of alirocumab).
- Availability of at least one calculated LDL-C value during the efficacy treatment period and within one of the analysis windows up to Week 12.

The efficacy treatment period is defined as the time period from the first injection of alirocumab up to the day of last injection +21 days.

